Summary of Revisions Made: Added COVID safety screen and other safety practices as outlined in the sunrise plan by PI [name] for all in-person visits. Added option of video conferencing for visit 1 and visit 3. Changed the plan for study drug supply to the participant. Now a 4-week supply of the study drug will be given to the participant on visit 2. Added abbreviated PK sample collection scheme for visit 4 (day 28) to be used during the COVID-19 pandemic. Added participants' choice of multiple needle sticks or placement of IV catheter on visit 4 when practicing abbreviated PK sample collection scheme.

Version Number: 6

Version Date: 18 September 2020

Summary of Revisions Made: Replaced consenting language to reflect template for e-consenting procedures. Corrected a discrepancy in consenting procedural description to reflect transition to e-consenting vs. in-person consenting procedures.

Version Number: 7

Version Date: 10 December 2020

Summary of Revisions Made: Moved BDI-II assessment to Study Day 0 (Consenting Visit) in order to obtain necessary randomization characteristics pre-MRI scanning on Day 1.

Version Number: 8

Version date: 21 February 2021

Summary of revisions: Added provision of partial compensation to participants based on the tasks completed in the study/visit, to accommodate scenarios where participants only complete a fraction of the planned activities.

Version Number: 9

Version date: 22 March 2021

Summary of revisions: Clarified eligibility language regarding “significant tissue damage” in order to use the same language between protocol and screening forms, moved SITBI to Day 0 activities in order to better inform eligibility determination, developed an online self-report REDCap survey for participant screening.

Version Number: 10

Version date: 05 May 2021

Summary of revisions: Assigned the WASI-II to be completed on Day 1 or 28. Remove BSS on Day 0 (only collect on Day 1 and 28) to limit patient burden. Added additional warning re: blood draw risks (fainting and/or dizziness) and additional common side effects of NAC (rash and itchiness). Removed language describing “medication boxes,” as study medications are provided in bagged, individual RX bottles at this time. Added language to specify that medication tracking diaries are only provided on Days 1 & 14 if the hardcopy option is elected by the participant. Changed final visit window from “28 +/- 3 dayfs” to “28-32 days,” to accurately reflect supply provided by IDS since COVID protocol changes. Additionally added flexibility to fill scripts up to 35 days if a participant is unable to complete final visit during 28-32 day medication supply window. Added detailed language regarding reporting of protocol deviations (per Advarra Handbook).

Version Number: 11

Version date: 01 July 2021

Summary of revisions:

(1) Clarified language describing more specifically when a participant may be withdrawn from the study due to suicidal ideation, moved text on study withdrawal from Section “6.2.5 Final evaluation” to Section “8. Intervention Discontinuation”, and edited that section for clarity.

(2) Added the role of an Independent Clinical Monitor, described in Safety sections 7.1 – 7.6 .

- (3) Removed the SITBI on Visit 4 to reduce participant burden.
- (4) Broadened inclusion /exclusion criteria to allow mild Alcohol Use Disorder, mild Cannabis Use Disorder, and Substance Use or Alcohol Disorders in early remission (at least 3 months of abstinence).
- (5) Clarified assessment of side effects and how they are evaluated as potential adverse events, added detail on monitoring procedure (emails sent to study team when triggered by threshold-level responses on key safety measures), and moved this text about side effects assessment from Section “6.2.4 Follow-up Visits” to Sections “7.1 Specification of Safety Parameters” and 7.2 “Methods and Timing for Assessing, Recording and Analyzing Safety Measures”.
- (6) Clarified 14-day pill count (will now be done by participant over Zoom on 14-day visit).
- (7) Deleted duplicated paragraph beginning with “Adverse Events, Unanticipated Problems and Serious Adverse Events”.
- (8) Added the definition of Unanticipated Problem.
- (9) Clarified language describing consent process to include dual authentication.

Version Number: 12

11.3	Participant Confidentiality	59
11.4	Study Discontinuation	60
12.	COMMITTEES.....	60
13.	PUBLICATION OF RESEARCH FINDINGS	60
14.	REFERENCES.....	60
15.	SUPPLEMENTS/APPENDICES.....	66
	I. Supplement I: Blood draw timing and blood processing	
	II. Supplement II: Neuroimaging procedures	
	III. Supplement III: Identification of Potential Participants	
	IV. Supplement IV: Procedure for suicide and self-harm risk assessment	

STUDY TEAM ROSTER

[name]	Principal Investigator	[contact]	[contact]	[name]
[name], MS	Research Coordinator	[contact]	[contact]	[name]
[name] PhD	Co-Investigator	[contact]	[contact]	[name]
[name]	Co-Investigator	[contact]	[contact]	[name]
[name]	Co-Investigator	[contact]	[contact]	[name]
[name]	Co-Investigator	[contact]	[contact]	[name]
[name]	Co-Investigator	[contact]	[contact]	[name]
[name]	Co-Investigator	[contact]	[contact]	Center for Magnetic Resonance Research University of Minnesota [name]
[name]	Co-Investigator	[contact]	[contact]	Center for Magnetic Resonance Research University of Minnesota [name]

PARTICIPATING STUDY SITES

University of Minnesota, Department of Psychiatry and Behavioral Sciences

PRÉCIS

Study Title

Identifying Biological Signatures of N-Acetylcysteine for Non-Suicidal Self-Injury in Adolescents and Young Adults

Objectives

Primary: To measure NAC-induced changes to concentrations of glutathione (GSH) in the anterior cingulate cortex (ACC) as measured by magnetic resonance spectroscopy (MRS) in 36 adolescents and young adults with NSSI (12 in each group: high, low, and placebo). Secondary:

- 1) Measure NAC-induced changes in the reduced-to-oxidized ratio of GSH (GSH/GSSG) in blood
- 2) Measure the NAC-induced changes to concentrations of glutamate (GLU) in the ACC as measured by MRS
- 3) Measure and compare tolerability of high dose NAC, low dose NAC and placebo
- 4) Characterization of NAC pharmacokinetics
- 5) Measure NAC induced biomarker changes in levels of the antioxidant proteins heme oxygenase-1 and catalase in blood.
- 6) Measure concentrations of GABA in the ACC by MRS.
- 7) Measure NAC induced biomarker changes in resting-state functional connectivity between amygdala and insula.

Design and Outcomes

This study is a double-blind, placebo controlled, 4-week course of two-tiered N-acetylcysteine (NAC) dosing focused on identifying the optimal dose to achieve meaningful change in measurable biomarkers (glutathione and glutamate).

This design will allow us to confirm acute biological changes, select the optimal dose for achieving biological effects, and examine dose/concentration-response relationships with respect to biological markers and pharmacokinetics.

Brief schedule of activities: Subjects will be recruited through community and clinical settings and screened using an online form. There will be a total of 4 in-person visits and two sets of on-line study activities.

- Day 0 -- Visit 1: Consent, clinical assessment, cognitive testing, randomization / group assignment
- Day 1 -- Visit 2: baseline measures, MRI scan, blood draw and begin study

medication

- Day 7: At-home online surveys
- Day 14: Visit 3: In-person visit, re-supply NAC/PBO
- Day 21: At-home online surveys
- Day 28 -- Visit 4 (final visit): NAC/PBO final dose, MRI scan, 5 blood samples via intravenous (IV) catheter for pharmacokinetic (PK) analyses, clinical assessment

Interventions and Duration

Eligible participants will be assigned to one of 3 groups (double-blinded): a low-dose NAC group (3600 mg/day), a high-dose NAC group (5400mg/day), and placebo (PBO). The study intervention period is 4 weeks. Total participation is up to 8 weeks, depending on the length of time between Day 0 and Day 1.

Sample Size and Population

We will recruit 36 adolescents and young adults aged 16-24 years. There will be 12 participants in each group (PBO, 3600mg/day, 5400mg/day). We will use a minimization procedure to ensure that the participants in these 3 groups will have similar age, clinical severity and medication status.

1. STUDY OBJECTIVES

1.1 Primary Objective

To test the hypothesis that oral NAC treatment (but not placebo) will lead to at least a 5% increase in glutathione (GSH) concentrations in the anterior cingulate cortex as measured by magnetic resonance spectroscopy (MRS) in a study of 36 adolescents and young adults with NSSI.

We will test two NAC doses (3600mg and 5400mg). Dose superiority will be defined both by change in GSH and by tolerability. Specifically, the superior dose will be the one which showed capability of achieving the greatest increase in GSH in the ACC as measured by MRS, and where no more than 20% of subjects at that dose discontinue or diminish their dose due to medication adverse effects (See section 5.1 for adverse effects and diminishing dose). (In other words, no less than 80% of subjects at a dose can discontinue or diminish their dose due to adverse effects in order to qualify as a superior dose.)

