9. STATISTICAL CONSIDERATIONS

9.1 General Design Issues

The goals of this study are to test whether significant change can be found in candidate biological signatures after 4 weeks of oral NAC. Three groups are used to compare pre-post treatment changes in those who received NAC 5400mg/day, 3600mg/day, or PBO.

Primary Hypothesis:

- 1) NAC high dose and/or NAC low dose (but not PBO) will increase cortical GSH by at least 5%

Secondary Hypotheses:

- 1) NAC high dose and/or NAC low dose (but not PBO) will decrease cortical GLU by at least 5%
- 2) NAC high dose and/or NAC low dose (but not PBO) will increase blood GSH/GSSG by at least 50%
- 3) NAC concentrations (using data from both dose groups) will be correlated with clinical and neuroimaging outcomes.
- 4) NAC high dose and/or NAC low dose (but not PBO) will increase resting-state functional connectivity between amygdala and insula
- 5) NAC high dose and/or NAC low dose (but not PBO) will increase ACC GABA.
- 6) NAC high dose and/or NAC low dose (but not PBO) will increase antioxidant protein levels (catalase and heme oxygenase-1 [HO-1]).
- 7) Higher-dose NAC will show larger changes in all of the biological signatures listed above compared to lower-dose NAC
- 8) While both NAC doses will be acceptable to most patients, lower-dose NAC will be better tolerated than higher-dose NAC.

Primary outcome measures:

- 1) GSH concentration in ACC

Secondary outcome measures:

- 1) Blood GSH/GSSG (the reduced-to-oxidized GSH ratio in blood)
- 2) Glu concentrations in ACC
- 3) Tolerability of NAC as measured using a side effects checklist
- 4) Pharmacokinetic analysis of NAC and its metabolites, CYS and GSH
- 5) Antioxidant protein levels (catalase and heme oxygenase-1 [HO-1]) for which

previous studies have shown increases following NAC treatment.

- 6) GABA concentrations in the ACC. Our pilot study found a significant increase in GABA levels after 28 days of oral NAC (6000 mg/day) ([name] et al. 2018).
- 7) Functional connectivity between amygdala and insula. Our pilot study showed that after treatment with oral NAC (3600 mg/day), participants with NSSI showed an increase in amygdala functional connectivity in a cluster that included the bilateral insula.

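### The section 1.1 dose rule can name a superior NAC dose when neither dose beats placebo, and names none if the dose with the larger GSH rise exceeds the 20% limit

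*Combined protocol and SAP*

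**What the plan says.** The primary objective (section 1.1) is to test whether oral NAC, but not placebo, raises GSH in the anterior cingulate by at least 5%. The same section then defines which of the two NAC doses is superior: "the superior dose will be the one which showed capability of achieving the greatest increase in GSH in the ACC as measured by MRS", together with a tolerability condition, "where no more than 20% of subjects at that dose discontinue or diminish their dose due to medication adverse effects". A parenthesis offered as a restatement reads "no less than 80% of subjects at a dose can discontinue or diminish their dose due to adverse effects", which contradicts that condition.

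Choosing the optimal dose is a stated purpose in the précis and in section 3. Section 9.1 predicts the direction of both criteria. Secondary hypothesis 7 is "Higher-dose NAC will show larger changes in all of the biological signatures listed above compared to lower-dose NAC". Secondary hypothesis 8 is "While both NAC doses will be acceptable to most patients, lower-dose NAC will be better tolerated than higher-dose NAC".

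Section 9.6 compares the three groups pairwise on percent change in GSH, with Tukey adjustment, or with the DSCF procedure if values are highly skewed. It adds that the effect size of each group's change will inform what is done next. Sections 9.1, 9.5 and 9.6 do not refer back to the dose rule.

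**The concern.** The rule leaves two gaps.

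1. **No placebo condition.** The rule ranks the two active arms against each other, and one of two means is always the larger. Placebo and the 5% level appear in the hypothesis, and tests against placebo appear in section 9.6, but nothing makes the dose choice depend on them.
2. **No fallback.** Both conditions attach to the same dose. If the arm with the larger rise exceeds 20%, it fails on tolerability and the other arm fails on greatest increase. No section says what happens then.

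This is the only dose-selection rule in the document. Followed as written, it can attach the word *superior* to a dose with no demonstrated effect, or select nothing when one dose works and is tolerated. The alternative is to choose how to read the rule after the data have been seen.

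**Working it through.** **The plan's own figures.** The plan gives no operating characteristics for the dose rule. The nearest figure is the power statement in section 9.2. Its alpha reproduces: 0.05/3 = 0.0167. The 80% power for a 2.95-point difference with 11 per group cannot be verified because no SD is given. Back-solving (two-sided, normal approximation) gives SD = 2.95 / [√(2/11) × (2.39 + 0.84)] = 2.95 / (0.426 × 3.23) = 2.14. This serves only to set an assumed SD below.

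**Inputs from the documents.** 12 per group (précis, section 5.1); 20% limit (section 1.1); up to 46 enrolled (section 4.3), so about 46/3 ≈ 15 per arm.

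**Assumptions.** True stop/reduce rates, dose-specific GSH changes and the SD. The documents give none of them.

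**Step 1: the limit in participants.** With 12 per arm, 2/12 = 17% passes and 3/12 = 25% fails. With 15 per arm, 3/15 = 20% passes and 4/15 = 27% fails. At a 10% true rate and n = 12, P(X ≤ 2) = 0.9¹² + 12(0.1)(0.9¹¹) + 66(0.01)(0.9¹⁰) = 0.282 + 0.377 + 0.230 = 0.889.

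**Step 2: no NAC effect.** All arms have zero true change and the same stop/reduce rate. If any larger mean counts, P(dose named) = P(X ≤ 2). If *increase* requires a positive mean, multiply by the chance that the larger of two independent means centred on zero is positive, 1 − ½ × ½ = 0.75. The last column comes from a simulation of 400,000 trials (11 analysed per arm for GSH, 12 for tolerability, SD 2.15). Results at SD 3.5 were practically the same.

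| True rate, each arm | P(X ≤ 2 of 12) | Named, any sign | Named, positive mean required | Positive mean required, named, neither dose beats placebo by Tukey |
|---|---|---|---|---|
| 5% | 0.980 | 98% | 74% | 72% |
| 10% | 0.889 | 89% | 67% | 65% |
| 20% | 0.558 | 56% | 42% | 41% |

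**Step 3: high dose has the larger rise.** No dose is named exactly when the high dose fails the limit.

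| True high-dose rate | 12 per arm, P(X ≥ 3) | 15 per arm, P(X ≥ 4) |
|---|---|---|
| 5% | 2% | 0.5% |
| 10% | 11% | 6% |
| 15% | 26% | 18% |
| 20% | 44% | 35% |
| 25% | 61% | 54% |

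The chance that no dose is named although the low dose passes the limit is P(high fails) × P(low passes). At true rates of 10% high and 5% low this is 0.111 × 0.980 = 11%. At 25% and 10% it is 0.609 × 0.889 = 54%.

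**Step 4: effect of ordering the rule and adding a placebo condition (simulation).** With no NAC effect and 10% rates, the chance of naming a dose falls from 67% to 1.6%. With assumed GSH changes of 7.5, 5 and 0% (high, low, placebo) and rates of 25% high and 10% low, it rises from 39% to 93%.

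**The case against.** **The predicted scenario.** A reader might infer that the rule breaks down in the very pattern the trial predicts. The documents do not support that. Hypotheses 7 and 8 predict direction only, and hypothesis 8 expects both doses to be acceptable to most patients. With 2/12 stopping or reducing on the high dose and 0/12 on the low dose, both predictions can hold and the high dose is named. The second gap is a sub-case of the predicted pattern.

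**Nine times in ten.** A reader might also take 89% as the chance of naming a dose when NAC does nothing. That figure ignores the word *increase*; requiring a positive mean gives 67% at the same assumed rate. Nor should high rates be used for one gap and low rates for the other: at 5% to 10%, where the first gap is largest, the second is only 2% to 11%.

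**Natural reading.** The parenthesis in section 1.1 speaks of what a dose needs to qualify as superior. That suggests tolerability is an eligibility condition, with the greatest increase chosen among eligible doses. This is a fair reading and would close the second gap. But the main sentence does not say it, and the parenthesis contradicts the limit it restates. The two readings give different answers.

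**Consequences.** The label is not an automatic decision to proceed. Section 9.6 tests each dose against placebo and uses effect sizes to inform next steps, and section 9.2 says the data will supply variability for a later confirmatory trial. This stands: the primary test and its error control are unaffected. It limits the severity but does not give the rule a placebo condition.

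**A significance gate is a choice.** Ranking doses without one is accepted in small dose-finding studies. This also stands, as a cost of the fix.

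**Conclusion.** The point holds in a bounded form. The section 1.1 rule can name a superior dose although neither beats placebo. It names none if the dose with the larger GSH increase exceeds the 20% limit, even when the other dose raises GSH and is tolerated.

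On the reading kinder to the plan (positive mean required), a trial with no NAC effect names a dose in about 74%, 67% and 42% of cases at true stop/reduce rates of 5%, 10% and 20%. The second gap ranges from 2% to 61% as the true high-dose rate goes from 5% to 25% with 12 per arm, and is somewhat smaller with 15 per arm.

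All these sizes rest on assumed rates and on a denominator that the documents do not fix. The two gaps themselves follow from the wording alone. Severity is moderate: a stated rule for a stated purpose can give a wrong or empty answer, but the primary hypothesis test is untouched.

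**What to change.** Rewrite the rule in section 1.1 as ordered steps, cross-refer to section 9.6, and settle it before unblinding. Keep the sponsor's 20% limit, and reconcile the parenthesis that contradicts it.

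- (a) Only doses meeting the limit are eligible. State which participants form the denominator.
- (b) An eligible dose is called superior only if its GSH change exceeds placebo in the Tukey or DSCF comparison already planned.
- (c) If both doses qualify, the one with the larger mean change is selected. If one qualifies, it is selected. If none does, report that no dose was selected. In that case, give the estimate and confidence interval for each dose against placebo.

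The cost is a few sentences; no new data or tests are needed. The downside is real: with about 11 to 12 per arm, a useful dose may miss step (b) and the trial may select none. On the plan's own power statement, a true difference of 2.95 points would be missed about 20% of the time (100% − 80%) at the Bonferroni level. The plan expects Tukey to do slightly better. The miss rate would be higher if variability exceeds that of the three healthy controls behind the calculation. Reporting the intervals keeps such a result interpretable.

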1.2 Secondary Objectives

- 1) Test the hypothesis that oral NAC will lead to an increase of at least 50% (degree of change will be greatest for NAC 5400mg, lesser extent for NAC 3600mg, minimal / no change for placebo) in the reduced-to-oxidized ratio of GSH (GSH/GSSG) in blood.
- 2) Test the hypothesis that oral NAC (but not placebo) will lead to a decrease of

at least 5% (degree of change will be greatest for NAC 5400mg, lesser extent for NAC 3600mg, minimal / no change for placebo) in the concentrations of glutamate (GLU) in the ACC as measured by MRS.

- 3) To measure tolerability of high dose NAC, low dose NAC and placebo
- 4) Characterization of NAC pharmacokinetics
- 5) To measure additional NAC-induced biomarker changes (degree of change will be greatest for NAC 5400mg, lesser extent for NAC 3600mg, minimal / no change for placebo) in blood sampling of antioxidant protein levels (catalase and heme oxygenase-1).
- 6) To measure additional NAC-induced biomarker changes in the concentrations of GABA in the ACC
- 7) To measure additional NAC-induced biomarker changes (degree of change will be greatest for NAC 5400mg, lesser extent for NAC 3600mg, minimal / no change for placebo) in brain imaging (resting-state functional connectivity between amygdala and insula).

2. BACKGROUND AND RATIONALE

2.1 Background on Condition, Disease, or Other Primary Study Focus

Non-suicidal self-injury (NSSI), the deliberate act of damaging one's own tissues without suicidal intent (Winchel and Stanley 1991). Onset of NSSI typically occurs in early-mid adolescence (Andover 2014; Andrews et al. 2013) and adolescent NSSI has an international prevalence of approximately 18% (Muehlenkamp et al. 2012). NSSI has been shown to predict negative outcomes such as persistent psychopathology and suicide attempts (Horwitz, Czyz, and King 2015; Tang et al. 2011; Victor and Klonsky 2014). Treatments for this habitual, self-destructive behavior pattern are sorely limited (Brent et al. 2013; Hawton et al. 2015). Since adolescence is notable for ongoing brain development (Giedd et al. 1999), it represents a critical window of opportunity to derail dangerous behavior trajectories, restore healthy behavior, and prevent negative outcomes (Paus, Keshavan, and Giedd 2008). Identification of novel, biologically-informed treatments for adolescent NSSI could improve health outcomes over the lifespan.

2.2 Study Rationale

N-acetylcysteine (NAC), a dietary supplement that is widely-available over-the-counter and by prescription, may have promise as a novel treatment for adolescent NSSI. NAC is the N-acetyl derivative of the amino acid L-cysteine. It can be found in health food stores with other natural products and also is a prescribed drug for conditions including Tylenol overdose and certain respiratory diseases. The pharmacokinetic (PK) properties of oral NAC have already been established in humans (Holdiness 1991). Several reviews have highlighted a growing literature suggesting that NAC can be helpful for a range of psychiatric disorders (Berk et al.

2013; Ng et al. 2008; Deepmala et al. 2015).

We conducted an open-label pilot study showed a reduction of NSSI frequency in adolescents after 8 weeks of oral NAC ([name] et al. 2018). These exciting findings prompted the proposed work taking next steps to investigate the possible use of this widely-available dietary supplement for a common and serious adolescent clinical problem.

In preparation for a definitive clinical NAC trial for adolescent NSSI, a critical preliminary step is to clarify NAC's biological signatures, or measures of the mechanisms underlying its clinical effects, to provide the basis for biologically-informed design of optimized efficacy trials. Literature to date (see review by (Berk et al. 2013) suggests two possible biological signatures for NAC's behavioral effects: (1) increasing glutathione (GSH), the primary antioxidant in the brain; and/or (2) modulating the glutamate (Glu)-cysteine antiporter (via cysteine [CYS], NAC's primary metabolite), effectively decreasing excessive Glu transmission. Both of these mechanisms could alleviate stress-induced neurotoxicities in adolescents with NSSI, but neither has been evaluated in NSSI. Based on current knowledge including our own past work, this study seeks to identify NAC's biological signatures in adolescents with NSSI, as follows:

- 1) Biological Signature #1: NAC increases GSH, a potent antioxidant. A key biological mechanism that has been proposed to underlie NAC's positive impact on mental health is via enhanced production of GSH, the primary antioxidant in the brain, providing a neuroprotective effect against the toxicities associated with stress (Berk et al. 2013; Ng et al. 2008). Oxidative stress mechanisms have been implicated in affective disorders (Siwek et al. 2013). In adolescents, NSSI behavior typically represents an attempt to self-regulate extreme levels of negative affect (Klonsky 2007). Furthermore, adolescents with NSSI frequently report a history of severe adverse experiences (Jacobson and Gould 2007) which themselves are known to have lasting adverse impacts on the CNS including neuronal damage (McEwen 2003; Goldwater et al. 2009; McEwen, Nasca, and Gray 2016; Lupien et al. 2009). Research in humans has shown that NAC preserves mitochondrial bioenergetics and normalizes GSH levels following spinal cord injury (Patel et al. 2014) and following brain injury (Pandya et al. 2014). A recent study of children with autism showed that NAC led to increased blood GSH levels compared to PBO (Wink et al. 2016). In a developmental animal model of schizophrenia (early hippocampal lesions in rats), NAC was shown to prevent brain and behavioral alterations induced by the lesions through diminishing oxidative stress (Cabungcal et al. 2014). In a mouse model of Parkinson's disease, mice with impaired cysteine uptake show evidence of oxidative stress and early cell death of dopaminergic neurons in the nigrostriatum; both processes were alleviated by NAC (Berman et al. 2011). Research in rodents has suggested that NAC leads to increased GSH redox ratios in brain tissue that persist after NAC is out of circulation (Zhou et al. 2015). Magnetic resonance spectroscopy (MRS) is capable of non-invasively measuring cortical GSH concentrations in-vivo, and systemic levels are typically

measured using the GSH redox ratio (GSH/GSSG). Despite the relevance of oxidative stress mechanisms to NSSI, no research to date has formally tested treatments targeting this system in adolescents with NSSI using appropriate methodology to confirm this potential biological signature.

- 2) Biological Signature #2: Glutamate (Glu) is the primary excitatory neurotransmitter in the brain, and excessive Glu signaling plays a key role in impaired synaptic plasticity and impaired regulatory control of impulses to engage in maladaptive behaviors (Kalivas and Volkow 2011, Brown et al. 1988). Since NSSI is a maladaptive, habitual behavior, it has conceptual overlap with other disorders along the impulsive/compulsive spectrum such as addiction, gambling, hair-pulling, skin-picking, and obsessive-compulsive disorder, in which dysregulation within the glutamate (Glu) system has been implicated (Kalivas and Volkow 2011). NAC regulates glutamate via the Glu-cysteine antiporter and previous studies have demonstrated that NAC may alleviate these impulsive/compulsive problems (Rothbart et al. 2013; McClure et al. 2014; Grant et al. 2016; Brown et al. 1988). NAC's primary metabolite cysteine (CYS) gets converted to cystine, which then enters glial cells in exchange for Glu via the Glu-cystine antiporter. Pre-clinical research on cocaine dependence showed that by this mechanism, NAC leads to increased extracellular glutamate via exchange of extracellular cysteine with intracellular glutamate, ultimately pumping glutamate out of glial cells (Baker et al. 2003; Moussawi et al. 2011). Increased concentrations of glutamate in the extracellular compartment serves to inhibit glutamate transmission ultimately serving to decrease glutamatergic neurotransmission (Moran et al. 2005) MRS is capable of non-invasively measuring cortical Glu concentrations in-vivo. While MRS cannot distinguish intracellular from extracellular Glu, it primarily measures intracellular Glu (R. Gruetter et al. 1998) Previous MRS research in adults with cocaine dependence showed that NAC led to decreased Glu in the anterior cingulate cortex (ACC; (Schmaal et al. 2012), a region of the brain that is implicated in regulating emotion and controlling impulses (Bush, Luu, and Posner 2000). In summary, a potential biological signature for NAC is its modulation of the Glu-cystine antiporter, downregulating excessive glutamate transmission and associated excitotoxicity. This biological signature can be indexed by MRS: decreased Glu concentrations in the ACC would indicate reduction in intracellular Glu concentrations due to NAC's modulation of the Glu-cystine antiporter. However, although the Glu system has been hypothesized as an important potential mechanism underlying NAC's behavioral benefits and in particular may be highly relevant to perpetuating NSSI, no studies have yet attempted to probe this system in adolescents with NSSI.

Finally, confirmation of NAC's biological signatures is challenging due its complex pharmacokinetics (PK). Oral NAC is primarily used in psychiatric studies because of its ease of use, but has low bioavailability (5-10%). While multiple PBO-controlled clinical trials have shown that oral NAC, typically at modest doses such as 1200mg-3000mg/day, produces significant behavioral changes in several psychiatric disorders (Berk et al. 2013), to date there is a paucity of evidence demonstrating that oral NAC

leads to significant direct antioxidant effects in the human central nervous system. Mental health studies have generally not included PK and pharmacodynamic (PD) components-- a missed opportunity to explain mixed findings with respect to clinical efficacy.

Summary and Scientific Premise: Adolescent NSSI is a severe clinical problem in need of new treatments. Results from an open-label pilot study suggest that NAC may be clinically useful in reducing frequency of NSSI in adolescents. Next steps in investigating this potential treatment will require a clear understanding of NAC's biological signatures and how they relate to behavior change. Based on existing knowledge, two candidate biological signatures for NAC include (1) increasing GSH in the brain, thus serving as an antioxidant, and (2) modulating Glu, serving to reduce stress-induced excitotoxicity. The current proposal will investigate these biological signatures of oral NAC in adolescents with NSSI using a study design that will address current knowledge gaps regarding the dose required to achieve PK and PD responses. Oral administration is selected for this study because of its ease of use and broader applicability in clinical practice. The proposed NAC doses are selected based on (1) our prior pilot study in adolescents with NSSI showed clinical improvement following an 8-week course of treatment of oral NAC at a dose of 3600mg/day ([name] 2018), and (2) our prior study in adults with neurological disease which showed changes in GSH following a 28-day course of treatment with oral NAC at a dose of 6000mg/day ([name] 2018). The 4-week period is selected to determine effects from acute oral NAC treatment on the brain, as was done in [name] et al 2018.

